Aim 1. A significant main effect for Treatment Condition for “delayed memory” would indicate differences between conditions in delayed memory. In particular, we expect that pairwise comparisons among the 3 treatment conditions (using the Sidak correction for multiple comparisons [this correction is available in SPSS’s mixed effects routine]) will show that 250 DCS and 100 modafinil significantly enhance delayed memory compared to placebo.

Aim 2: A significant interaction between Treatment Condition and Time will indicate that differences between delayed recall in the “drug context” (week 3) vs. “no-drug context” (week 4) are different for different treatment conditions. Dummy variable coding for treatment condition, comparing modafinil to each of the 2 other treatment conditions, is expected to show significantly greater reduction of recall memory between weeks 3 and 4 for those taking modafinil compared to other conditions due to the change in drug context in week 4.

Aim 3: We hypothesize a Treatment Condition main effect for immediate memory, such that pairwise comparisons among the 3 conditions (using the Sidak correction for multiple comparisons) will show that 250 DCS and 100 modafinil will significantly enhance immediate memory compared to placebo.

Exploratory Analyses: We will examine whether baseline antidepressant use, mood (BDI-II), fatigue (FSS), attentional/executive function (COWAT, TMT-B), HVLT total score, and/or digits backward performance moderates active study drug effects relative to the placebo condition. Examination of associations between performance on immediate memory scores and delayed recall (including ICAT performance at Weeks 2-4) will also be examined in each study drug condition to help clarify the nature of in-session memory augmentation vs. retention effects across the weeks of testing. The effect of treatment condition on BDI will also be examined using the same analysis as Aim 1 (including pairwise comparisons among the groups). We expect BDI to be enhanced in 100 Modafinil, and explore whether it will also be enhanced in 250 DCS. We will also examine if improved memory mediates the changes in BDI.

Power Analysis. We used PinT 2.12 (a program to calculate effect sizes in mixed models) to calculate the smallest N necessary to detect a medium effect size ($d=.5$) with .80 power for the

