specific hypothesized comparisons in Aims 1, 2, and 3. We conservatively assumed that 15 covariates (including interaction terms between covariates and both Treatment Condition and Time) will be included as additional predictors in each analysis (the power is greater if no interaction terms are necessary). We also assumed 10% attrition by week 4, although the mixed effects models include all participants regardless of missing data. Since there are multiple comparison tests, we used the conservative Bonferroni correction and set the p level at $.05/3=.0167$. **Aim 1:** A total sample size of 77 is necessary to detect a medium effect with .80 power. **Aim 2:** A sample size of 59 is necessary to detect a medium effect size for the interaction between time and individual treatment contrasts. **Aim 3:** Since the analysis in Aim 3 is identical to that in Aim1, 77 participants are required for Aim 3. Thus, a total sample size of 77 will give us at least .

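### Does correcting for all three pairs in Aims 1 and 3, when only the two placebo contrasts are predicted, waste power?

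*SAP*

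**What the plan says.** - **SAP, Aim 1.** The analysis looks for a Treatment Condition main effect, which "would indicate differences between conditions in delayed memory". It then makes "pairwise comparisons among the 3 treatment conditions (using the Sidak correction for multiple comparisons"). The stated expectation is that "250 DCS and 100 modafinil significantly enhance delayed memory compared to placebo".
- **SAP, Aim 3.** The structure is the same: "We hypothesize a Treatment Condition main effect for immediate memory", followed by Sidak-corrected pairwise comparisons. The expectation is that "250 DCS and 100 modafinil will significantly enhance immediate memory compared to placebo".
- **SAP, Aim 2.** The Treatment Condition by Time interaction is examined with contrasts "comparing modafinil to each of the 2 other treatment conditions", so modafinil is compared directly with DCS.
- **SAP, Exploratory Analyses.** The Aim 1 analysis, including its pairwise comparisons, is applied to the BDI.
- **SAP, Power Analysis.** Power is for the "specific hypothesized comparisons in Aims 1, 2, and 3". On multiplicity, "we used the conservative Bonferroni correction and set the p level at" .05/3 = .0167. Aims 1 and 3 need 77 participants for .80 power at d = .5; Aim 2 needs 59.

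**The concern.** Aims 1 and 3 each name two expected results, and neither predicts anything for DCS against modafinil. The Power Analysis says it serves the hypothesised comparisons, yet it divides .05 by three. In a three-arm trial of 77 participants planned at .80 power with no stated margin, a correction for an unpredicted comparison seems to take power from the two that matter. A reader could conclude that a change of wording alone would recover up to 4.5 points of power per contrast, with no added participants or visits.

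**Working it through.** **Inputs.** From the SAP: three arms, per-comparison level .05/3, power .80, d = .5, total N = 77. Assumed because not stated: two-sided tests and equal allocation.

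**The plan's own figures.** .05/3 = .0167 reproduces. N = 77 cannot be checked. A plain two-sided comparison of two means at .0167 and d = .5 needs 84 per arm, or 252 in total. Reaching 77 needs a residual variance factor of about 77/252 = .31, which depends on mixed-model inputs the SAP does not report. The stated .80 is therefore taken as given.

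**Levels per contrast.**
- Sidak over three: 1 − .95^(1/3) = .01695 (z = 2.388)
- Sidak over two: 1 − .95^(1/2) = .02532 (z = 2.237)
- Dunnett, two contrasts correlated .5: z = 2.212, level .0270

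The analysis level (.01695) and the planning level (.0167) are practically the same, and planning used the slightly stricter one. The two sections agree.

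**Where the 5% goes, per outcome.** Under the three-pair rule, the chance of any false claim is about 4.5% over all pairs and 3.2% over the two placebo contrasts. So DCS against modafinil accounts for about 4.5 − 3.2 = 1.3 points, and 5.0 − 4.5 = 0.5 point is unused slack.

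**Power per placebo contrast, no gate.** Noncentrality = 2.394 + .842 = 3.236; power = 1 − Φ(z − 3.236).
- Sidak over three: .802
- Sidak over two: .841
- Dunnett: .847

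**Power if the main effect must be significant first** (simulated, chi-square on 2 df at .05).

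| Other drug | Sidak-3 | Sidak-2 | Dunnett |
|---|---|---|---|
| Full planned effect, or none | .801 | .835 | .840 |
| Half the planned effect | .797 | .814 | .816 |

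**Cost in false claims.** The SAP analyses three delayed-recall measures separately and states no correction across them. The chance of at least one false placebo-contrast claim, with assumed outcome correlation from .7 to 0, is:

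| Rule | No gate | With gate |
|---|---|---|
| Sidak-3 | 7.4–9.2% | 7.1–8.8% |
| Sidak-2 | 10.6–13.4% | 8.3–10.4% |
| Dunnett | 11.2–14.2% | 8.4–10.5% |

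Aim 3 adds three immediate-memory measures (digit span, HVLT, ICAT). For six independent measures without a gate, which is the upper end, the chance is:
- Sidak-3: 1 − (1 − .032)^6, about 18%
- Sidak-2: 1 − (1 − .047)^6 = 25.1%
- Dunnett: 1 − (1 − .050)^6 = 26.5%

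**Other valid rules that keep all three pairs.**
- *Main effect as a gate, then unadjusted pairs.* With exactly three groups this controls the per-outcome error over all pairs. Power is .877 when the other drug has the full effect or none, and .827 when it has half. Both exceed the gated two-contrast rules (.835–.840 and .814–.816).
- *No gate, step-down.* Once any pair passes Sidak-3, the others are tested at .05. Power is .865 with the other drug at full or no effect, above .841–.847. At half effect it is .815, which is below them.

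**The case for a change.** The best case for narrowing the family is that the mismatch lies in the SAP's own wording: two predictions per aim, power for the hypothesised comparisons, and a divisor of three. The arithmetic behind it is sound. At the stated .80 the gain is real, no participants are added, and with a single outcome the error of the two placebo contrasts would stay within 5% (4.7% with Sidak-2, 5.0% with Dunnett). If true power is below .80, which cannot be ruled out because N = 77 cannot be reproduced, the Sidak-2 gain without a gate could reach about 6 points.

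That much stands, but it does not show a fault. Stating two expectations does not oblige a plan to test only those two. The SAP chooses all pairs for Aims 1 and 3, carries the same approach to the BDI, and contrasts modafinil with DCS in Aim 2, so interest in that pair is plausible. Nor is the change free: it gives up one controlled comparison and raises the false-claim rate across several outcomes.

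Two ambiguities remain. The SAP does not say whether the main effect is a gate. The protocol's Research Design and Methods section names cognitive therapy content and logical memory as primary, whereas the SAP analyses three delayed-recall measures. Neither makes the three-pair correction wrong. The second is a reason not to loosen it in isolation.

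**Conclusion.** The concern does not hold. Sidak over three pairs is valid and slightly conservative, matches the level used for sample size, and is already allowed for in the stated .80 power. Correcting over two contrasts would gain 3.9 to 4.5 points per contrast without a gate and 1.7 to 3.9 with one. In exchange, DCS against modafinil would lose its error-controlled test, and the false-claim rate over three independent delayed-recall measures would rise from 9.2% to 13.4–14.2% without a gate, or from 8.8% to 10.4–10.5% with one. Rules that keep all three pairs give more power in most of the scenarios examined, so the two-contrast correction is not clearly the better design. Competent statisticians could choose either way. These figures assume two-sided tests, equal arms, a normal approximation and the SAP's .80 at .0167; the false-claim rates also depend on outcome correlations the documents do not give.

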### Randomization and Study Drugs

Participants will be block randomized (by sex and SSRI use) to one of the **3** drug conditions. Study drugs will be provided in identical capsules. Patients will receive one capsule of their randomized drug on Study Visit 2 and one capsule on Study Visit 3. At these visits, study capsule administration will be observed and precede cognitive testing by 90 minutes. Similar timing has been the standard in our studies of DCS augmentation; and is appropriate to the absorption and half-life of modafinil (Darwish et al., 2010).

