### **Procedures**

- **Visit 1: Screening and Baseline Assessment.** Following phone screening, patients will be scheduled for an evaluation session where informed consent will be obtained. The psychiatric evaluation begins with the Structured Clinical Interview (SCID) to evaluate the presence of psychiatric inclusion and exclusion criteria. Patients will also complete a medical history form and interview with the study physician. If inclusion criteria are met, baseline questionnaires and cognitive assessment :administration of the WMS--Logical Memory (Story A), Digit Span, Hopkins Verbal Learning Test, Trails A and B, and the Controlled Oral Word Association Test (see below). Participants will then be scheduled for 3 subsequent weekly assessment sessions, with randomization in a double-blind fashion using a random number list to receive one of the 4 study conditions. Randomizations will be blocked by sex and SSRI use and will occur at week 2.
- **Visit 2: Study Drug Administration and Assessment.** At this visit, patients will first complete the BDI and FSS followed by administration of the randomized study capsule 90 minutes before initiation of cognitive testing procedures. During the waiting period, magazines and television videotapes will be provided. Drug adverse effects will be queried at the end of this waiting period for symptoms over the last hour as well as emergent symptoms occurring after the last study session. For cognitive testing, participants will listen to the WMS Logical Memory story B, followed by immediate recall. Similar procedures will then be followed for the Emotional Logical Memory Task. Participants will then complete unique versions (to the study week) of Digit Span-Backwards, HVLT, and ICAT. Finally, participants will complete a 45min portion of computerized CBT providing an overview of cognitive therapy and experience with cognitive errors.
- **Visit 3: Study Drug Administration and Assessment.** Study drug administration and assessment procedures match Visit 2, but with the addition of one-week delayed recall of both the WMS Logical Memory story B and the Emotional Logical Memory Task. CTAS and SoCT are specific to the previous week's content, and a novel 45min portion of computerized CBT (cognitive schema work) is presented.

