- **Visit 4: Final Assessment.** No study drug is administered. Participants will first complete the BDI and FSS followed by one-week delayed recall of the WMS Logical Memory story B, followed by one week delayed recall of the Emotional Logical Memory Task. Then, in turn, each story will be retold, and followed by an immediate recall session. Participants will then complete the Cognitive Therapy Awareness Scale (for the previous weeks CBT content) **and SoCT** followed by a unique Digit Span-Backwards, HVLT, and ICAT.

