STATISTICAL ANALYSIS PLAN

for

Improving Therapeutic Learning in Depression: Proof of Concept
NCT02376257

Date of Document: November 15, 2013

[name] et al. DCS, Modafinil, PBO: Data Analysis

Analyses for outliers, non-normal distributions, nonlinear relations, and influence statistics will be conducted; data transformations will be considered where appropriate. We will perform repeated-measures ANOVAs using mixed-effects regression models (MRMs) in SPSS 20.0 to analyze the data. The MRM approach to repeated measures ANCOVA allows inclusion of all participants regardless of missing data (which improves power and generalizability), can model the covariance matrix of the repeated measures more flexibly than ANCOVA, and is the recommended method for longitudinal data analysis (Hamer & Simpson, 2009). The ANCOVA will consist of 3 levels of the between-subjects IV (Treatment Condition) and 2 (or 3) levels of the within-subjects IV (Time). For delayed recall memory, Time will represent weeks 3 and 4, when recall for information presented at the previous session will be assessed. Three separate analyses will be performed, one for each of the 3 measures of delayed recall memory; retention of 1) cognitive therapy principles, 2) emotional narrative, and 3) WMS Story B (exploratory analyses will also examine cognitive therapy skill use, following this analytic approach). For immediate memory, Time will represent weeks 2 & 3, the time points of primary interest for the immediate memory tests (digit span, HVLT, ICAT). Scores on the baseline memory assessments (week 1) and baseline antidepressant use will be included as covariates in all analyses. Since the relation between the covariates and outcome may be different among treatment conditions (e.g., the relation between baseline memory and drug influenced memory may be lower for 250 DCS and 100 modafinil compared to placebo), interaction terms will allow these relations to vary across treatment conditions. Similarly, because the relation between the covariates and the DVs may be lower at weeks 2 and 3 (with drug ingestion) compared to week 4 (no drug ingestion), interaction terms will also allow these relations to vary across Time. Non-significant interaction terms will be dropped.

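### Aim 2 reads a larger modafinil fall in recall from week 3 to week 4 as a drug-context effect, but acute drug action stops at the same time, so at least against placebo the cause is not identified

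*SAP*

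**What the plan says.** **Aim 2 (SAP).** A Treatment Condition by Time interaction is to show that "differences between delayed recall in the “drug context” (week 3) vs. “no-drug context” (week 4) are different for different treatment conditions". Modafinil is then compared with each of the other two arms, and the expected result is a greater fall in recall "for those taking modafinil compared to other conditions due to the change in drug context in week 4". No other explanation is named.

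**Drug state at each visit (Protocol).** Under Randomization and Study Drugs, at Visits 2 and 3 "study capsule administration will be observed and precede cognitive testing by 90 minutes". Under Procedures, for Visit 3, "Study drug administration and assessment procedures match Visit 2, but with the addition of one-week delayed recall" of the two stories. Visit 4 is drug-free.

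**Acute effect (SAP, Aim 3).** The hypothesis is that "250 DCS and 100 modafinil will significantly enhance immediate memory compared to placebo".

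**Immediate-memory tests.** At Visit 4 the therapy-content measures are "followed by a unique Digit Span-Backwards, HVLT, and ICAT". The SAP's model for these tests stops a week earlier: "For immediate memory, Time will represent weeks 2 & 3, the time points of primary interest for the immediate memory tests". The exploratory analyses do use ICAT at weeks 2 to 4, but only in associations between immediate scores and delayed recall within each drug condition.

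**The concern.** Material recalled at week 3 was learned on drug and is retrieved on drug. Material recalled at week 4 was learned on drug and is retrieved off drug. Two mechanisms therefore predict a larger modafinil fall:

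- **Context:** what was learned on modafinil is harder to retrieve without it.
- **Loss of acute enhancement:** modafinil helps performance, including retrieval, on the day it is taken, and that help is absent at week 4.

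The second lies close to the trial's own Aim 3. Placebo participants have no acute effect to lose, so the placebo contrast cannot separate the two.

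The readings differ for augmenting CBT. The first says that learning on modafinil transfers poorly to the drug-free state. The second says only that the drug helps on the day.

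**Working it through.** **1. The plan's own figure.** The SAP gives 59 participants for .80 power to detect d=.5 in the Aim 2 interaction, with the p level set at .05/3=.0167. It states no within-person correlation and no variance explained by covariates, so 59 cannot be reproduced. For two groups with SD 1, two-sided, n = 2[(z for .0167 + z for .80)/.5]² = 84 per arm, or 252 in three arms. On a change score with variance 2(1−ρ), a total of 59 needs ρ of about .88 (59 analysed) to .89 (59 less 10%). Nothing below depends on this figure. Taken at face value, it means that with 77 participants a purely acute loss of d=.5 would make an individual contrast significant at least about 80% of the time.

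**2. What each contrast estimates.** Write e for the encoding benefit, a for the acute effect on retrieval, and c for the context cost, all in SD units.

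- Modafinil delayed recall: e + a at week 3, e − c at week 4. Fall = a + c.
- Placebo: fall = 0. The modafinil-placebo contrast is a + c.
- The modafinil-DCS contrast is (a + c) minus the same sum for DCS.
- New-item immediate tests with acute effect a′: fall = a′, with no context term.
- Delayed minus immediate, against placebo: a + c − a′, which equals c only if a = a′.

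Expected contrasts, confirmed by simulation:

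| Scenario | Delayed, vs placebo | Delayed, vs DCS | Immediate, vs placebo |
|---|---|---|---|
| Context only, c=.5 (modafinil) | .50 | .50 | .00 |
| Acute only, a=.5; DCS none | .50 | .50 | .50 |
| Acute only, a=.5; DCS .25 | .50 | .25 | .50 |
| Acute only, a=.5; DCS .5 | .50 | .00 | .50 |

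**3. Chance of a significant result with no context effect.** Inputs from the SAP: 77 participants, 10% attrition, d=.5 (its planning effect, borrowed here for the acute effect). Assumptions: equal arms, so n = 77 × .9 / 3 = 23.1; two-sided normal approximation; no covariates; ρ as shown. SE = √[2 × 2(1−ρ)/n]. For both contrasts together, a bivariate normal with correlation .5 is used, because the modafinil arm is shared.

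| ρ | SE | Placebo contrast, p<.05 | Placebo contrast, p<.0167 | Both contrasts p<.05: DCS acute effect none / half / equal |
|---|---|---|---|---|
| .5 | .294 | .40 | .24 | .24 / .10 / .02 |
| .7 | .228 | .59 | .42 | .43 / .17 / .02 |
| .8 | .186 | .77 | .62 | .64 / .25 / .025 |
| .9 | .132 | .97 | .92 | .94 / .47 / .025 |

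At d=.3 the placebo contrast gives .26 to .63 at p<.05 for ρ from .7 to .9.

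**4. What the week 4 immediate tests can add.** In the simulation (26 per arm, p<.0167), one immediate-memory contrast with a true acute loss of .5 has power of about .25 at ρ=.5 and .65 at ρ=.8. For delayed minus immediate, take the mean of the three tests, assume that their changes correlate .3 with each other, and set ρ=.7. If the delayed change is uncorrelated with that mean, the SE is .28. If the correlation is .3, the SE is .24. For a true context effect of .5, power is about .43 to .55 at p<.05 and .27 to .38 at p<.0167.

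**The case against.** The strongest reply has four parts.

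- **Expectation, not rule.** The causal clause sits inside a statement of what the sponsor expects, and the preceding sentence describes the interaction neutrally. A reader might infer that the SAP commits to calling any larger modafinil fall a context effect. It does not. What stands is that context is the only explanation offered and that nothing is planned to examine another.
- **DCS as comparator.** Aim 3 predicts acute enhancement for DCS too, and Aim 2 expects modafinil to fall more than each of the other arms. A reader might infer that acute loss reproduces the whole Aim 2 pattern. That follows only if DCS has little or no acute effect. With equal acute effects, both contrasts are significant only about 2% of the time. This part stands. However, the documents do not show that the acute effects are equal, and the SAP does not require both contrasts to be significant.
- **Week 4 data are not ignored.** ICAT at weeks 2 to 4 is named in an exploratory analysis meant to clarify in-session augmentation versus retention, so it would be wrong to say that the week 4 tests are left out altogether. But an association within an arm does not estimate a difference between arms in week 3 to week 4 change. Week 4 Digit Span-Backwards and HVLT have no explicitly planned treatment comparison.
- **Imperfect control.** These tests use new items in one session, not week-old material. They inform on acute loss but cannot cleanly separate it from context. This stands and limits the remedy. The week 4 immediate story recall is no cleaner, because the stories have been heard before.

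**Conclusion.** The concern holds in limited form. Week 3 versus week 4 confounds drug context with acute drug action, so a larger modafinil fall, at least against placebo, does not by itself support the context attribution.

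Its size depends on assumptions that the documents do not settle: an acute effect that extends to retrieval, its magnitude, the between-week correlation, and DCS's acute effect. For a purely acute d=.5, the placebo contrast would be significant with probability .40 to .97 at p<.05 over correlations of .5 to .9. The pair of contrasts ranges from about .02 to .94, depending mainly on DCS.

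These should not be read as inflated type I error: under acute loss the interaction is truly non-zero, and what goes wrong is its interpretation. No sample size or primary estimate turns on the point. It is worth correcting because Aim 2 is a named and powered hypothesis and the data that bear on it are already scheduled.

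**What to change.** In SAP Aim 2:

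1. Pre-specify, as a supportive analysis, the modafinil-versus-placebo and modafinil-versus-DCS contrasts of week 3 to week 4 change for Digit Span-Backwards, HVLT and ICAT. Report them with confidence intervals beside the delayed-recall contrasts.
2. Report the standardised difference between the delayed-recall and immediate-memory contrasts with its confidence interval, for example using the mean of the three standardised tests as in the working.
3. Replace the causal phrase with: *consistent with a change in drug context or loss of acute on-drug enhancement*. Favour context only if the interval for that difference excludes zero, on the side of a larger delayed-recall fall, and both Aim 2 contrasts point the same way. A rule asking only whether the delayed fall is the larger would be met about half the time when the true falls are equal.

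**Cost.** Wording and three further models on data already collected, with no new visit, test or participant. The context claim becomes harder to make: power for the difference is roughly .4 to .55 at p<.05 for a true context effect of .5, assuming ρ=.7. A null immediate-memory contrast will not rule out acute loss, and the comparison assumes similar acute effects on new-item tests and on one-week retrieval. If the extra analyses are not wanted, the wording change alone should still be made.

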## D. RESEARCH DESIGN AND METHODS

---

We propose to study cognitive function and memory performance over 4 study sessions in **77** men and women with major depression, who, in a double-blind fashion, will be randomly assigned to either: (1) 250mg DCS, (2) 100mg modafinil, or (3) placebo administered on Study Weeks 2 and 3. The design calls for baseline assessment (Week 1), followed by two weekly sessions when randomized study drug is administered, and a final week (Week 4) when retention is assessed under the conditions of no study drug. The drugs under study may have differential effects on immediate recall at the time the drug is taken vs. retention effects one week later. As such, the memory tests include both items unique to a given study week (i.e., the ICAT, digits backward, and HVLT), and memory tasks that are repeated over time (i.e., narrative memory tasks and the cognitive therapy content). Primary outcomes will be cognitive therapy content and retention of logical memory (with exploratory examination of CBT skill use).

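### The SAP's one analysis meant to separate in-session gains from retention works within each arm on different material, and does not specify the on-drug, same-story immediate recall that the protocol collects

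*SAP*

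**What the plan says.** - **The question.** Protocol section D states: "The drugs under study may have differential effects on immediate recall at the time the drug is taken vs. retention effects one week later". The same section separates "items unique to a given study week (i.e., the ICAT, digits backward, and HVLT") from tasks repeated over the weeks, which include the narratives.
- **The analysis given to it.** Under Exploratory Analyses, the SAP relates immediate scores, with the ICAT through week 4 among them, to later recall. It says that these associations "will also be examined in each study drug condition to help clarify the nature of in-session memory augmentation vs. retention effects". No contrast between arms is stated.
- **The immediate tests.** The opening paragraph of the SAP's data analysis text sets weeks 2 and 3 as "the time points of primary interest for the immediate memory tests (digit span, HVLT, ICAT").
- **The delayed outcomes.** The same paragraph says "Three separate analyses will be performed, one for each of the 3 measures of delayed recall memory": cognitive therapy principles, the emotional narrative and WMS Story B. Covariates are Week 1 memory scores and baseline antidepressant use.
- **What is collected on drug.** Protocol, Procedures, Visit 2: testing starts 90 minutes after the capsule, and "participants will listen to the WMS Logical Memory story B, followed by immediate recall". For the emotional story, "Similar procedures will then be followed for the Emotional Logical Memory Task". Visit 3 repeats the Visit 2 procedures and adds one-week delayed recall. Visit 4, without drug, has delayed recall, a retelling of each story and a further immediate recall.
- **What the SAP does not say.** Immediate recall of either story is not named as an outcome, covariate or mediator. The only mediation analysis named runs from memory to BDI.

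**The concern.** A higher delayed score on drug can arise in two ways: the participant took in more of the story on the day, or lost less of it over the week. To tell these apart, one needs immediate and delayed scores on the same material, compared between arms. The planned associations provide neither. An immediate-delayed correlation within one arm describes how participants rank on two tasks. It does not say whether the drug moved either score, and three separate correlations do not test whether the arms differ.

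At stake is the interpretation of mechanism. A positive Aim 1 result could not be assigned to encoding or retention, and chance differences between three small-sample correlations could be read as drug effects. The validity of the Aim 1 test is not affected.

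**Working it through.** **Inputs.** Total N of 77, three arms and 10% attrition by week 4 come from the SAP. Equal allocation is an assumption, since the ratio is not stated: 77/3 = 25.7, about 26 per arm, and 0.9 × 77/3 = 23.1, about 23 after attrition. The plan gives no figure for these associations. N = 77 enters only as the source of the arm size and is not disputed here.

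**1. Precision within one arm.** The 95% interval is tanh(atanh r ± 1.96/√(n−3)).
- r = .4, n = 26: .01 to .68.
- r = .3, n = 26: −.10 to .62; n = 23: −.13 to .63.

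**2. How often separate verdicts disagree when the arms do not differ.** Assume the same true correlation ρ in all three arms, n = 26 each, and each arm judged at two-sided .05. With p the chance that one arm is significant (by simulation), the chance that the arms are neither all significant nor all non-significant is 1 − p³ − (1−p)³.

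| ρ | p | mixed verdict, n = 26 | mixed verdict, n = 23 |
|---|---|---|---|
| .2 | .165 | 41% | 38% |
| .3 | .324 | 66% | 62% |
| .4 | .543 | 74% | 75% |
| .5 | .766 | 54% | 62% |
| .6 | .923 | 21% | 30% |

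At ρ = .4, for example, 1 − .543³ − .457³ = .744. The formula peaks at .75 when p = .5, so ρ = .4 is close to the worst case. The documents give no value for ρ.

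**3. A direct comparison of two correlations.** For 80% power at two-sided .05, the Fisher-z gap must be (1.96 + 0.84) × √(2/(n−3)), which is 0.83 at n = 26 and 0.89 at n = 23. That means, for example, .30 against about .81 to .83. Comparing correlations properly removes the false contrasts but has little power.

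**4. Whether the associations could separate the mechanisms at all.** All settings here are assumptions: an encoding shift of 0.5 SD, a slope of delayed recall on encoding of 0.7, another immediate task correlated 0.3 with encoding, and no drug effect on that task. The retention-only drug is set to give the same delayed gain, 0.7 × 0.5 = 0.35. A simulation with 400,000 per arm gave:

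| Quantity | Encoding-only drug | Retention-only drug |
|---|---|---|
| Within-arm r, other task with delayed recall (placebo, drug) | .21, .21 | .21, .21 |
| Arm difference, same-story immediate recall | 0.50 | 0.00 |
| Arm difference, delayed recall | 0.35 | 0.35 |
| Delayed difference adjusted for the other task | 0.35 | 0.35 |
| Delayed difference adjusted for same-story immediate recall | 0.00 | 0.35 |

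The within-arm correlation is 0.3 × 0.7 = .21 whichever way the drug acts, so it carries no information on the question. The two rows using same-story immediate recall do separate the cases. With measurement error of SD 0.5 in immediate recall, the adjusted encoding-only difference is 0.35 − 0.7 × (1/1.25) × 0.5 = 0.07 rather than zero, so adjustment is then incomplete.

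**5. Two substitutes that do not work.** A Treatment × Delay interaction on raw scores would be 0.35 − 0.50 = −0.15 for the encoding-only drug, which would look like impaired retention. A Treatment × immediate-score interaction tests whether slopes differ, and under these settings they do not differ for either mechanism.

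**The case against.** The strongest reply is that the SAP already compares arms. Aim 1 does so on delayed memory and Aim 3 on immediate memory, both with Sidak pairwise tests, and Aim 2 tests Treatment × Time. The associations are a supplementary exploratory look in a proof-of-concept study. This stands as far as it goes: a reader might infer that the plan has no between-arm comparison on the immediate side, and that would be wrong. But the tests listed for immediate memory are not the stories, so an Aim 3 result cannot be linked to retention of the stories.

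Three other stronger readings are not supported.
- *The immediate tests are unrelated to delayed recall.* The protocol describes the HVLT as a verbal memory test and says the battery was chosen for functions that may bear on retention of CBT. The documents support only that the material is different.
- *The SAP excludes story immediate recall.* The exploratory sentence refers to immediate memory scores in general terms, and the earlier list sets the time points for the immediate-memory model. Story recall may have been intended. It is not explicitly specified, and one sentence would settle it.
- *Three quarters of trials would show false differences.* The 74% applies near the worst-case correlation and assumes that each arm is declared significant or not and the verdicts compared. The SAP says only that associations will be examined.

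**Conclusion.** The point holds as a limit on an exploratory analysis. As written, the within-arm associations cannot separate encoding from retention, and they do not test whether arms differ. Mixed verdicts from identical arms would occur in about 21% to 74% of trials for ρ from .2 to .6, assuming 26 per arm, equal allocation, a common correlation and a .05 verdict in each arm.

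A reader might infer that data already collected allow the split for every outcome. They do not. No immediate test of CBT content is described, so the CTAS, a primary outcome, cannot be divided this way. Only the two stories can. Even there, the stories appear to be presented again at Visit 3, so Week 4 delayed recall follows two exposures. Week 3 delayed recall takes place at a drug visit, so an effect on retrieval may be mixed with retention. The matter is minor: no aim, primary test or sample size is affected.

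**What to change.** Amend the SAP's exploratory section, for Story B and the emotional story only:

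1. Name same-story immediate recall as an exploratory outcome. Compare arms on it at weeks 2 and 3 with the Aim 3 mixed model, and show the result beside the Aim 1 arm contrasts on delayed recall of the same story.
2. Report the arm contrast in delayed recall with and without adjustment for same-story immediate recall, with intervals. Use Visit 2 immediate recall with Week 3 delayed recall as the main pair, because it precedes the apparent second presentation.
3. If immediate-delayed associations are compared across arms, fit one model with all arms, and do not set separate within-arm results against each other. This compares slopes and should not be offered as a test of encoding against retention.

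State the limits with the results: low precision at this size; adjustment conditions on a post-randomization score that is measured with error, and assumes no unmeasured confounding; Week 3 recall is at a drug visit; the CTAS cannot be split.

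The cost is a few sentences of SAP text and a little analysis of data that the protocol already collects. No confirmatory test is added.
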